Clinical Development

RAD001

CRAD001C24114 / NCT00767819

Multicenter, triple-arm, single-stage, phase II trial to determine the preliminary efficacy and safety of RAD001 in patients with histological evidence of progressive or metastatic bone or soft tissue sarcomas

RAP Module 3 – Detailed statistical methodology

Author:

[REDACTED]

Document type: RAP Documentation

Document status: Final 1.0

Release date: 07-Jul-2011

Property of Novartis
Confidential

May not be used, divulged, published or otherwise disclosed
without the consent of Novartis

Novartis approval signatures for:

RAP Module 3 – Detailed statistical methodology

Signature

Date

Signature

Date

1 Data analysis

This was a non-randomized, multicenter, triple-arm, phase II trial evaluating the treatment of RAD001 in the following three arms: in patients with progressive or metastatic bone or soft tissue sarcoma (except for GIST), in patients with progressive or metastatic GIST after failure or intolerance of treatment with imatinib or sunitinib, and in patients with progressive or metastatic alveolar soft part sarcoma (ASPS), respectively.

The study was designed to assess the activity, safety, and tolerability of the therapy with RAD001 in progressive bone or soft tissue sarcoma in the **three** arms each.

The data were analyzed by Novartis. Any data analysis carried out independently by the investigator(s) was recommended to be submitted to Novartis before publication or presentation. It was planned that the data from participating centers in this protocol were combined within each of the arms, so that an adequate number of patients was available for analysis.

Data were summarized with respect to demographic and baseline characteristics, efficacy observations and measurements, safety observations and measurements, and pharmacokinetic measurements. Categorical data were presented as absolute frequencies and percentages. For continuous data, N (the number of valid observations), N miss. (the number of missing observations), mean, standard deviation, median, minimum, and maximum were presented.

It was planned that the data of each arm were to be analyzed and reported independently of the other arm once the number of patients needed for analysis was reached. However, the methods described in this analysis plan apply for all three arms, if not otherwise indicated.

For simplification, populations for analysis, and the analysis of patient demographics/other baseline characteristics, treatment, primary and secondary efficacy variables, and safety were described without referring to a specific arm. As mentioned above, the methods of analysis were applied to each arm separately.

Changes from the analysis pre-planned in the protocol:

1. Although planned in the protocol, the central radiologic review was only incompletely performed due to a variety of reasons (no images submitted from local to central radiologist, when already the first tumor assessment resulted in an overall lesion response of 'progressive disease'; or images were not assessable according to the central radiologist). An incomplete sequence of central assessments cannot be used to derive the primary and secondary efficacy variables. Thus, the trial will be analyzed based on local tumor assessments only.
2. The intention-to-treat (ITT) set will be used for the primary efficacy analysis rather than the per-protocol (PP) set, since this is what is recommended by RECIST criteria (version 1.0, see [Therasse et al. 2000](#): 'All patients included in the study must be assessed for response to treatment, even if there are major protocol treatment deviations or if they are ineligible. [...] All conclusions should be based on all eligible patients.')

1.1 Populations for analysis

The **safety set** consisted of all patients who received at least one dose of study drug and had at least one post-baseline safety assessment. Patients were analyzed according to treatment received. Of note, the statement that a patient had no adverse events also constituted a safety assessment.

The **intent-to-treat (ITT) set** consisted of all patients who received at least one dose of study drug and had at least one post-baseline assessment of the primary efficacy variable (target/non-target lesion assessment according to RECIST). Patients without any post-baseline assessment of tumor were included if they were defined as progressive disease based on clinical evaluation.

The **per-protocol (PP) set** consisted of all patients of the intent-to-treat population who did not show any major protocol violations. As major protocol violations were considered those that may have an impact on the study outcome. Criteria that were assumed to have such an impact were defined in a Review Meeting before database lock.

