****This list of clinically relevant drug interactions is updated as of December 02, 2009****

6.3.6 Study drug discontinuation

Study drug must be discontinued for a given patient if the investigator determines that continuing it would result in a significant safety risk for that patient. Patients who, in the opinion of the investigator, require alternative medical therapy, will be discontinued from the study. Patients with a progression will be discontinued from the study. Patients who become pregnant during the study must be withdrawn. If the treatment has to be interrupted for more than 21 consecutive days for any reason, the patient will be discontinued from the study unless otherwise discussed with the study coordinator. In case of patient's discontinuation, the end of study evaluation will be completed as soon as possible. End of study evaluations will include adverse events, concomitant medications and therapies, physical examination, vital signs, ECOG performance status, biochemistry, hematology and tumor measurement.

Patients who discontinue prematurely due to significant AE should continue to be followed-up until resolution of the AE, and the relevant sections of the CRF should be completed as appropriate. Patients who are discontinued due to clinically significant abnormalities in clinical laboratory results should continue to be evaluated until the abnormality resolves or is judged to be permanent.

It will be documented whether or not each patient completed the clinical study. If, for any patient, the study treatment was discontinued the reason will be recorded. Reasons that a patient may discontinue participation in a clinical study are considered to constitute one of the following:

1. Adverse event(s)
2. Abnormal laboratory value(s)
3. Abnormal test procedure result(s)
4. Unsatisfactory therapeutic effect
5. Subject's condition no longer requires study treatment

6. Protocol violation which affect the safety of the patient
7. Subject withdraws consent
8. Lost to follow-up
9. Administrative problems
10. Death

Progressive disease is defined as unsatisfactory therapeutic effect.

For patients who are lost to follow-up, the investigator should show “due diligence” by documenting in the source documents steps taken to contact the patient, e.g. dates of telephone calls, registered letters, etc.

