7.1 Information to be collected on screening failures

Information on screening failures will be kept in the Novartis Screening Failure Log. No CRF has is needed for screening failures.

All data obtained from the assessments listed in Table 1 and described in detail in the subsections below must be supported in the patient’s source documentation. Assessments that generate data for database entry and which are recorded on CRFs are listed using the CRF name. Assessments that are transferred to the database electronically (e.g. laboratory data) are listed by test name.

The final examination (visit 6 respectively EOS) will be performed for all patients included in this trial (i.e. who signed an informed consent form and received study treatment), whether they discontinued study treatment prematurely or completed the study treatment. Patients who discontinue study drug before completing the core study, and those who prematurely withdraw from the core study for any reason, should be scheduled for the End-of-study-visit as soon as possible, at which time all of the assessments listed for the EOS-visit will be performed.

During the follow-up period, the treatment regimen as taken during the study should be maintained. However, changes in the regimen based on each patient’s clinical needs and the investigators’ experience and discretion will be possible at any time. In the Follow-Up-Phase

	Base-line ¹	Core study						Follow-up ¹²				End of FUP
Visit No.	1	2	3	4	5	6	EOS	FUP 1 - X				
Day	-14	1										
Week			4	8	12	16		28	40	52	X	
Tumor evaluation (RECIST) ⁷	x			x		x	x	x	x	x	x	
Study drug administration		x	x	x	x	x		x	x	x	x	
Adverse events ⁸	x	ongoing data capture						ongoing data capture				
Prior medication	x											
Concomitant medication	x	ongoing data capture						ongoing data capture				
Survival-information ¹⁰												x
Comments		ongoing data capture						ongoing data capture				

¹Described in Section 7.2; 7.5.2

²Described in Section 7.5.3

³Described in Section 7.5.4

⁴Described in Section 7.5.5

⁵Described in Section 7.5.7; 8.2

⁶Described in Section 7.5.6

⁷Described in Section 7.4

⁸Described in Section 8.1.1

⁹Chest x-ray only in cases where no CT/MRI thorax is available

¹⁰Survival information for patients who discontinued earlier

¹¹ Baseline assessment can be done between day-14 and day 1 together with visit 2

¹² During the follow up period patients will continue to be followed every 3 months until progression

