10.1 Populations for analysis

The Safety Population will consist of all patients who received at least one dose of study drug and had at least one post-baseline safety assessment. Patients will be analyzed according to treatment received. Of note, the statement that a patient had no adverse events also constitutes a safety assessment.

The intent-to-treat (ITT) population will consist of all patients who received at least one dose of study drug and have at least one post-baseline assessment of the primary efficacy variable (assessment according to RECIST). Patients without any post-baseline assessment of tumor will be included if they are defined as progressive disease based on clinical evaluation.

The per-protocol (PP) population (i.e. the efficacy-analyzable population) consists of all patients of the intent-to-treat population who show no major protocol violations. As major protocol violations are considered those that may have an impact on the study outcome. Criteria that are assumed to have such an impact will be defined in a Review Meeting before database lock.

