1.4 Analysis of the primary objective(s)

1.4.1 Variable

The primary variable is defined as the proportion of patients in whom a best overall response of complete (CR) or partial (PR) response or stable disease (SD) was observed at 16 weeks according to RECIST (version 1.0, [Therasse et al. 2000](#)) based on local radiologic assessments.

The best overall response for each patient was determined from the sequence of overall (lesion) responses at Visit 4/Week 8 and Visit 6/Week 16, respectively, according to the following rules (see Post-text supplement 1 to the study protocol):

- CR = at least two determinations of CR at least 4 weeks apart before progression.
- PR = at least two determinations of PR or better at least 4 weeks apart before progression (and not qualifying for a CR).
- SD = at least one SD assessment > 6 weeks after start of treatment (and not qualifying for CR or PR).
- PD = progression or death due to underlying cancer ≤ 16 weeks after start of treatment (and not qualifying for CR, PR or SD). Patients with symptoms of rapidly progressing disease without radiologic evidence will be classified as progression only when clear evidence of clinical deterioration is available and patient discontinued due to 'Disease progression'. Furthermore, patients without radiologic evidence for progression who were prematurely discontinuing from the study for 'unsatisfactory therapeutic effect', 'new cancer therapy' or 'death' (from any reason) will be classified as progression.
- UNK = all other cases (i.e. not qualifying for confirmed CR or PR and without SD after more than 6 weeks or early progression within the first 16 weeks)

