1.4.2 Statistical hypothesis, model, and method of analysis

The best overall response rate (CR/PR/SD/PD/UNK) was presented together with the appropriate two-sided confidence interval for the ITT set. Since the one-sided alpha was set to 10%, two-sided 80% confidence intervals were presented. Exact confidence intervals were computed according to the method of Clopper and Pearson.

The absolute number of patients showing a best overall response of CR, PR or SD was determined to conclude preliminary activity or non-activity of the study drugs in this patient population according to the rules outlined in CSP [section 10.2](#). Furthermore, the lower limit of the confidence interval was used to support the decision in favor of p_0 or p_1 : if the lower limit of the confidence interval overlapped p_0 , the hypothesis that p is greater than or equal to p_1 could be rejected; on the other side, if the lower limit of the confidence interval excluded p_0 , the hypothesis that p is greater than or equal to p_1 could be accepted.

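### The SAP's ITT set drops treated patients with no post-baseline scan and no clinical PD, against the RECIST rule cited for it; any such exclusion can only favour the drug

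*SAP*

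**What the plan says.** In the list of changes from the protocol (SAP section 1), the primary analysis moves from the per-protocol set to the ITT set. The reason given is a quotation from RECIST: "All patients included in the study must be assessed for response to treatment, even if there are major protocol treatment deviations". The quotation goes on to say that conclusions should rest on all eligible patients.

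SAP 1.1 then defines the ITT set as patients who took at least one dose and "had at least one post-baseline assessment of the primary efficacy variable (target/non-target lesion assessment according to RECIST". The one exception is for patients with no post-baseline tumor assessment who are judged progressive on clinical evaluation. Protocol 10.1 has the same restriction ("have at least one post-baseline assessment of the primary efficacy variable (assessment according to RECIST"), but there the primary analysis was per-protocol.

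Other relevant provisions:

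- **Response categories (SAP 1.4.1).** SD needs at least one SD assessment more than 6 weeks after start. CR and PR each need two determinations. The SAP also counts as progression "patients without radiologic evidence for progression who were prematurely discontinuing from the study for" unsatisfactory effect, new cancer therapy or death from any reason. A residual category exists: "UNK = all other cases (i.e. not qualifying for confirmed CR or PR and without SD after more than 6 weeks".
- **Decision (SAP 1.4.2 and 1.6).** The responder count decides: at least 11 of 36 in arm I, at least 8 of 24 in arm II. In addition, "the lower limit of the confidence interval was used to support the decision in favor of" p0 or p1, using a two-sided 80% Clopper-Pearson interval.
- **End-of-study scan.** Protocol 7.1: "The final examination (visit 6 respectively EOS) will be performed for all patients included in this trial". Protocol 6.3.6: "In case of patient's discontinuation, the end of study evaluation will be completed as soon as possible", and that evaluation includes tumor measurement.

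**The concern.** The set does not do what its stated justification requires. A dosed patient who stops for toxicity, withdrawn consent or loss to follow-up before any post-baseline scan, with no clinical progression, is not in the denominator.

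The direction of the error is known in advance, because an unscanned patient cannot be a responder. The only other set planned for the week-16 primary result is the per-protocol set (SAP 1.4.4). It is a subset of the ITT set, so it cannot show the effect.

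There is also an ambiguity. SAP 1.1 does not say whether unscanned progression under 1.4.1 counts as progression on clinical evaluation. A patient who dies before the first scheduled scan at week 8 may have no end-of-study scan, so entry to the set depends on how the reader links the two sections.

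At stake are the reported rate, its interval and the supporting interval check.

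**Working it through.** **1. Reproduce the design.** Inputs from SAP 1.6: p0 = 20%, p1 = 40%; n = 36 with cut-off 11; n = 24 with cut-off 8. Exact binomial tails:

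- Arm I: P(X ≥ 11 | 36, 0.20) = 0.0889; type II error 1 − P(X ≥ 11 | 36, 0.40) = 1 − 0.9096 = 0.0904.
- Arm II: P(X ≥ 8 | 24, 0.20) = 0.0892; type II error 1 − P(X ≥ 8 | 24, 0.40) = 1 − 0.8081 = 0.1919.

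These match the stated 8.9% / 9.0% and 8.9% / 19.2%.

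**2. Direction.** With N treated, k excluded and x responders, the plan reports x/(N − k) instead of x/N, and x does not depend on k. For x ≥ 1 the rate and both limits rise with k. For x = 0 the rate and lower limit stay at zero and only the upper limit rises.

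**3. Size.** The documents give neither k nor x. Assume N = 36 and 24, and take x one below each cut-off, where the interval check is most sensitive. The lower limit L of the two-sided 80% Clopper-Pearson interval is the 10% quantile of Beta(x, n − x + 1), with n = N − k.

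| Excluded k | Arm I rate | L | Arm II rate | L |
|---|---|---|---|---|
| 0 | 10/36 = 27.8% | 18.0% | 7/24 = 29.2% | 17.0% |
| 1 | 10/35 = 28.6% | 18.6% | 7/23 = 30.4% | 17.8% |
| 2 | 10/34 = 29.4% | 19.1% | 7/22 = 31.8% | 18.7% |
| 3 | 10/33 = 30.3% | 19.8% | 7/21 = 33.3% | 19.6% |
| 4 | 10/32 = 31.3% | 20.4% | 7/20 = 35.0% | 20.7% |

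Up to three exclusions, the interval check and the count rule agree. At four (4/36 = 11% of arm I, 4/24 = 17% of arm II) the lower limit excludes 20% while the count rule says inactive.

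**4. Count rule.** With 36 and 24 treated, exclusions leave x unchanged, so the type I error stays at 8.9% in both arms.

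**5. If withdrawn patients are replaced (Protocol 5.2).** The number treated can then exceed 36 or 24. Keeping the cut-offs and taking the 20% null to hold for all treated patients:

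- Arm I: P(X ≥ 11 | 37, 0.20) = 10.5%, and 12.2% at 38. Lower limit at 11/37 = 19.8%. Power at 37 is 92.8%.
- Arm II: P(X ≥ 8 | 25, 0.20) = 10.9%, and 13.1% at 26. Lower limit at 8/25 = 19.6%. Power at 25 is 84.6%.

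The documents do not say that the 20% null refers to all treated patients; SAP 1.6 words the design in evaluable subjects.

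Protocol section 10 makes arm III descriptive only, so no decision rests on it.

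**The case against.** The strongest reply is that little depends on this. The design is sized in evaluable subjects, withdrawn patients are replaced, and the count rule does not move. The end-of-study tumor evaluation is required of every treated patient, and clinical progression is added back, so the excluded group may be empty. The two rules conflict only with at least four unreplaced exclusions and a count at the boundary. A count of exactly 10/36 has probability 7.9% at p = 0.20 and 4.5% at p = 0.40; for 7/24 the figures are 10.0% and 9.6%. All of this stands, and it limits the size of the problem.

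A second reply is that the RECIST quotation was there to justify not dropping patients for protocol deviations, which the set achieves. It also speaks of eligible patients, and an all-treated set does not test eligibility. This is partly fair, but a treated, eligible patient without a scan is still excluded, which neither part of the quotation supports. The UNK rule in SAP 1.4.3 does not help, since it classifies patients without bringing unscanned ones into the set.

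A third reply is that an all-treated denominator with fixed cut-offs can itself bring the two rules into conflict after a single replacement. That is true at the boundary, and it is a real cost of the fix. It does not justify the current definition, because the disagreement comes from unassessed patients whom the present set keeps out of view.

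**Conclusion.** The concern holds. The ITT definition contradicts the reason given for making it primary, and any exclusion works in one direction only. The effect is probably small and may be nil: about 1 point in the rate per excluded patient near the boundary, and a conflict between the two decision aids only from four exclusions. This rests on 36 and 24 treated, no replacement, and boundary counts of 10 and 7, all of which are assumptions. The deciding count rule is not affected under them. It should be corrected because the repair is simple and no planned analysis would reveal the effect on the rate.

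**What to change.** In SAP 1.1:

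- Define the primary set in each arm as all patients who received at least one dose of study drug.
- State that unscanned progression under 1.4.1 is included as PD.
- Class patients with no post-baseline tumor assessment and no PD under 1.4.1 as UNK and count them as non-responders. Compute the rate and 80% interval on that denominator.
- Keep the present set as supportive, renamed evaluable, and report the number it excludes, with reasons.
- Keep the cut-offs of 11 and 8. If more than 36 or 24 patients were treated, do not reset them, because SAP 1.5.1 shows that response outcomes were already known when the SAP was written. Report instead the exact type I error of the fixed cut-off at the number treated, stating that it assumes a 20% null for all treated patients.

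The cost is SAP wording, a minor extra analysis, and a slightly lower reported rate if anyone was excluded and there is any responder. If replacement took the treated number above plan, the type I error on all treated patients exceeds the 10% target, and at the boundary the interval check can disagree with the count rule. Both should be reported as they are. Planned power is not reduced.

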1.2 Patient demographics/other baseline characteristics

Demographic and background information were summarized for the ITT set, using frequency distributions for categorical variables and descriptive statistics of mean, standard deviation, minimum, median and maximum for continuous variables. Background information included prior medication, past/current medical conditions, diagnosis and extent of cancer, ECOG performance status and tumor evaluation at baseline.

Medical history was coded using MedDRA and was presented by system organ class, and MedDRA preferred term. Separate tables were provided for past medical condition and current medical condition. Prior medications (including prior antineoplastic medications and radiotherapy) were coded according to WHO Drug Reference List (WHO-DRL). Prior medications were summarized by ATC class and preferred term.

1.3 Treatments (study drug, rescue medication, other concomitant therapies, compliance)

Study drug and concomitant therapies were analyzed for the safety set.

Study drug

Duration of exposure to study drug was defined as the time from start of treatment to the last end date documented in the Study Drug Administration CRF. Duration of exposure was summarized descriptively.

Mean daily doses of study drug were calculated including and excluding zero doses for periods of temporary interruption of treatment regardless of whether this was due to safety reasons or patients' non-compliance. Mean daily doses were summarized descriptively.

The number of dose changes/patients with dose changes (including temporary dose interruption) was presented by reason for dose change by frequency distribution. Permanent treatment discontinuations were analyzed by frequencies.

Concomitant medications

Concomitant medications were coded according to WHO-DRL and summarized by ATC class and preferred term using frequency tables.

